9.1.2. Secondary Design - SCRI Design with Post-Vaccination Control Interval

In addition, the SCRI design uses information from cases (ie, individuals who experience a safety event following vaccination) to compare the risk interval following vaccination to post-vaccination non-risk intervals ("post-vaccination control interval") in the same individual. AGAT Only ABRYSVO vaccinated individuals who experience an outcome of interest within the risk or control interval will contribute to the SCRI analysis. As the SCRI design is a within person analysis, it implicitly controls for time fixed confounders. Time varying confounders still need to be controlled for, but with short, defined risk windows the risk of time varying confounding is limited.

To ensure all individuals have the same chance of having a confirmed diagnosis, the SCRI analysis will require individuals to have continuous enrollment in VHA benefits for an additional 30 days following the risk and post-vaccination control interval (eg, a total of 40 days of follow-up comprised of the day 0-3 risk interval [including the day of ABRYSVO vaccination], day 4-10 control interval, and additional 30 days of follow up). Note that a longer control interval of 7 days (ie, day 4-10 corresponding to the day 0-3 risk interval and day 2-8 corresponding to the day 0-1 risk interval) will be used to increase power of detecting an association should one truly exist by providing a more statistically stable estimate of the baseline risk while avoiding the confounding impact of time-varying covariates (eg, seasonality, other vaccination, medication use). Since the required post-vaccination follow-up period is short, this requirement is not expected to produce any appreciable selection bias in the analysis.

The SCRI design with a post-vaccination control interval is presented in Figure 1 below.

Figure 1. Example of SCRI Design for Assessment of a Safety Event with a 0-3 Days Risk Interval in the ABRYSVO Cohort*

^{*} Figure is not drawn to scale.

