9.2.1. Inclusion Criteria

Three cohorts will be defined for the main analyses.

- A. A cohort of individuals who received ABRYSVO will form the ABRYSVO cohort and must have:
 - A record for at least one dose of ABRYSVO in the study period from 31 May 2023 (or earliest date of vaccine availability for the indicated population) to 31 May 2026; the date of ABRYSVO vaccination will define the index date for this cohort
 - o No record of an RSV vaccine from a manufacturer other than Pfizer
- B. A cohort of individuals who did not receive ABRYSVO but received another vaccine will form the contemporary vaccinated control cohort and must have:
 - A record for another vaccine (eg, influenza vaccine, COVID-19 vaccine, and other pre-specified vaccines such as shingles, hepatitis B listed in Section 9.3.3) within 30 days of a corresponding ABRYSVO vaccinee's vaccination date; the control's index date will be the date of the control's non-RSV vaccine
 - No record for any RSV vaccine on the index date or in the baseline period (ie, 2 years prior to the index date)
 - Individuals in the vaccinated control cohort who go on to receive an RSV vaccine following their index date will be censored at the time of RSV vaccination. If the RSV vaccine is ABRYSVO, these individuals will contribute to the ABRYSVO cohort starting from the date of ABRYSVO receipt.
- C. A cohort of individuals who did not receive ABRYSVO or another vaccine on the index date but had at least one vaccination record in the year prior to the index date will form the contemporary unvaccinated control cohort and must have:
 - No record for any RSV vaccine on or within 30 days of the index date or in the baseline period (ie, 2 years prior to the index date)

- No record for any other vaccine (eg, those listed in Section 9.3.3) on or within 30 days of the index date
 - This cohort will be assigned an index date matched to a corresponding ABRYSVO vaccinee's vaccination date. If the vaccination is associated with a healthcare encounter (ie, inpatient [IP] or outpatient [OP] visit), the unvaccinated control will be required to have a healthcare encounter within 30 days of the assigned index date, and the date of the healthcare encounter will be set as the index date for the unvaccinated control.

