9.2.3. Subgroups

Safety surveillance may be conducted for subgroups of interest as applicable to each age group, including, but not limited to the ones described below.

The following subgroups will be analyzed for the 18-59 years old age group and the 60 years and older age group:

- Individuals in VA priority group 1; These individuals have either the highest levels of service connected disability (≥50% disabling), are considered unemployable, or have received the medal of honor. Individuals categorized as priority group 1 are the highest priority for VHA care. This will ensure that the individual is more likely to receive all of their care from a VA facility;
- Females enrolled in the VHA (pending sufficient sample size);

• Individuals with co-administration with other vaccines (ie, influenza vaccine, COVID-19 vaccine, or other pre-specified vaccines [eg, shingles, hepatitis B] listed in Section 9.3.3) on the same day.¹⁸

The following subgroups will be analyzed for the 60 years and older age group only:

- Individuals with specific conditions that increase the risk for severe RSV as defined by the CDC during the baseline period; list of conditions may be updated to align with the most current CDC definition at the time of data analysis (see Section 9.2.1);
- Different age groups defined by age on the index date, eg, 60 to 69 years, 70 to 79 years, ≥80 years;
- Individuals enrolled in the VHA with dual coverage who are also identified in the Centers for Medicare & Medicaid Services (CMS) Medicare administrative claims data, which will be linked to the Corporate Data Warehouse (CDW) to supplement the data for a more complete evaluation of healthcare encounters.

Additional subgroups of interest may be assessed as additional information becomes available from ongoing clinical trials, Vaccine Adverse Event Reporting System (VAERS), and other sources that will inform the ABRYSVO safety profile.

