A conditional Poisson regression model will be used to compare the rates of safety events in the risk interval vs post-vaccination control time period. From this model, we will report rate ratios and 95% CIs that will be interpretated as the relative incidence for the safety event in the risk interval compared to the control interval.

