9.7.2.5. Analysis of Risk Factors for Atrial Fibrillation

If an increased risk of atrial fibrillation following ABRYSVO vaccination is observed from the analyses described above, a risk factor analysis will be conducted via logistic regression among individuals vaccinated with ABRYSVO. Specifically, up to ten baseline characteristics will be selected a priori (eg, age, sex, race/ethnicity, history of atrial fibrillation prior to baseline period, co-administration of influenza vaccine, COVID-19 vaccine, or other pre-specified vaccines such as shingles, hepatitis B] listed in Section 9.3.3) and included in a multivariable logistic regression model with atrial fibrillation as the outcome to determine if any of the select baseline characteristics may be risk factors associated with atrial fibrillation.

Co-administration with other vaccines and patient characteristics during the two-year baseline period (or based on all available data for history of atrial fibrillation) will also be

described to enhance understanding of the healthcare profiles of atrial fibrillation cases. Co-administration will be defined as receipt of ABRYSVO and another vaccine (ie, influenza vaccine, COVID-19 vaccine, or other pre-specified vaccines [eg, shingles, hepatitis B] listed in Section 9.3.3) on the same day.¹⁸

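### The SCRI control interval cannot avoid confounding by vaccines given on the same day as ABRYSVO, so the all-recipient ratio is not specific to ABRYSVO

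*Protocol*

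**What the plan says.** Section 9.1.2 sets the SCRI windows as "day 4-10 corresponding to the day 0-3 risk interval and day 2-8 corresponding to the day 0-1 risk interval". It explains that the 7-day control interval gives a stable baseline while "avoiding the confounding impact of time-varying covariates (eg, seasonality, other vaccination, medication use". Earlier in the same section there is a caveat: "Time varying confounders still need to be controlled for, but with short, defined risk windows the risk of time varying confounding is limited". No method of control is given there.

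On who contributes, Section 9.1.2 says "Only ABRYSVO vaccinated individuals who experience an outcome of interest within the risk or control interval will contribute to the SCRI analysis". The vaccine-related bar on entering the ABRYSVO cohort in Section 9.2.1 is "No record of an RSV vaccine from a manufacturer other than Pfizer", so a same-day influenza or COVID-19 vaccine does not exclude a recipient.

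Section 9.7.2.3 fits a conditional Poisson model to "compare the rates of safety events in the risk interval vs post-vaccination control time period" and states no term for another vaccine.

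Section 9.7.2.5 begins its definition "Co-administration will be defined as receipt of ABRYSVO and another vaccine" and requires both on the same day. Section 9.2.3 lists one related subgroup: "Individuals with co-administration with other vaccines (ie, influenza vaccine, COVID-19 vaccine, or other pre-specified vaccines". Recipients of ABRYSVO without a same-day vaccine are not listed. Section 9.9 sets out the strengths of the SCRI and does not mention same-day vaccines among its limits.

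**The concern.** A self-controlled design removes what is constant within a person. It separates two time-varying exposures only if their timing differs. Two vaccines given on day 0 have identical risk and control days in every person who receives both, so no choice of control-interval length can tell their effects apart. Shortening the interval helps only against vaccines given on other days.

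The protocol expects same-day vaccination: it is defined, it is a subgroup, and it is a field in the case line listing (Section 9.1.3). The study is a post-marketing commitment about one product, and the SCRI is the design offered as free of between-person confounding. A reader who takes Section 9.1.2 at its word would attribute the all-recipient ratio to ABRYSVO alone, although it is a joint estimate whenever another vaccine was given that day.

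**Working it through.** **Inputs from the protocol.** Risk interval days 0-3 (4 days) and control interval days 4-10 (7 days), from Section 9.1.2 and Table 1. Background rate at age 60 and over 33.9 per 1,000 person-years, one-sided alpha 0.05 and power 80%, from Section 9.5.1. Table 3, days 0-3: 156 events, 84 of them in the control interval, and N = 129,204 for RR 1.5; 787 events for RR 1.2. Reporting by rate ratio and 95% CI, from Section 9.7.2.3.

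**Assumed, because the protocol gives no figure.** c, the share of recipients with a same-day vaccine, and r, that vaccine's own ratio for atrial fibrillation in days 0-3. The background rate is taken as equal with and without co-administration.

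**Step 1: reproduce Table 3.** N = control events / (rate × 7/365) = 84 / (0.0339 × 7/365) = 129,204, as stated. The method that the table note names (signed-root likelihood), with a 4-day risk and a 7-day control interval, gives 155 events for RR 1.5 (stated 156) and 784 for RR 1.2 (stated 787). The figures thus rest on a 4-day risk interval, which is used below. They contain no allowance for co-administration.

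**Step 2: expected ratio when ABRYSVO has no effect.** With background rate λ per day and N recipients:

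- risk-interval events = 4λN[(1 - c) + c·r]
- control-interval events = 7λN
- rate ratio = (1 - c) + c·r = 1 + c(r - 1)

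The length of the control interval cancels, so changing it does not reduce the bias.

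| c | r = 1.0 | r = 1.5 | r = 2 |
|---|---|---|---|
| 25% | 1.00 | 1.125 | 1.25 |
| 50% | 1.00 | 1.25 | 1.50 |
| 75% | 1.00 | 1.375 | 1.75 |

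**Step 3: how often a ratio of 1.25 would be flagged.** Given the total number of events, the count in the risk interval is binomial. Its share is 4/11 = 0.364 under no effect and (4 × 1.25)/(4 × 1.25 + 7) = 5/12 = 0.417 at a ratio of 1.25. An exact two-sided 95% CI excludes 1 on the upper side when the one-sided exact test has p ≤ 0.025.

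| Events | Needed in risk interval | P(flag), 95% CI | P(flag), one-sided 0.05 |
|---|---|---|---|
| 156 | 70 | 0.23 | 0.34 |
| 787 | 314 | 0.85 | 0.92 |

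The 95% CI column matches the planned reporting. The one-sided 0.05 level appears in the protocol only for sample size. The 787-event row corresponds to 718,310 recipients aged 60 and over in Table 3.

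**Step 4: size of an ABRYSVO-alone stratum.** For that stratum to reach 129,204 recipients, the total needed is 129,204/(1 - c): 172,272 at c = 25%, 258,408 at 50% and 516,816 at 75%.

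**The case against.** **The sentence concerns changes during follow-up.** Section 9.1.2 is explaining why the control interval is 7 days, and it names other vaccination beside seasonality and medication use. The same section admits that time-varying confounders need control. This is fair, and it makes the error one of scope. But the wording has no limit to other days, the caveat comes with no method, and Section 9.9 does not add one.

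**Co-administration is already handled.** A reader might infer that the protocol ignores it in the SCRI. It does not. Section 9.7.3 repeats the safety analyses in the Section 9.2.3 subgroups, and Section 9.7.2 counts the SCRI among them, so a co-administered SCRI is foreseen, subject to feasibility. With no other term in the model, ABRYSVO-alone counts could be found by subtracting co-administered from all-recipient counts. That works only if interval counts are reported for both, which is not promised. The co-administered stratum by itself gives the joint effect. The risk-factor model in Section 9.7.2.5 runs only after a signal and is not a within-person analysis.

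**The rest belongs in the SAP.** The subgroup list is open and the SAP may add strata. This stands for the missing stratum taken alone. It does not excuse a statement in the protocol that is wrong for same-day vaccines.

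**The bias is hypothetical.** A reader might infer that another vaccine's effect will be reported as ABRYSVO's. The documents do not support that: it requires r to differ from 1, and no r is given. Nor do they support the reading that a null result would hide an ABRYSVO effect. That needs a co-administered vaccine that lowers atrial fibrillation risk in days 0-3, and nothing in the protocol suggests one.

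**Conclusion.** The concern holds in a limited form. The claim in Section 9.1.2 can be right for vaccines given on other days and is wrong for same-day vaccines. The all-recipient SCRI ratio estimates the effect of ABRYSVO together with whatever was given that day, and no listed analysis isolates ABRYSVO.

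The numerical consequence is illustrative. With no ABRYSVO effect the ratio is 1 + c(r - 1). It is 1.25 at the assumed c = 50% and r = 1.5, and a 95% CI would then flag it in about 23% of studies at 156 events. At r = 1 it is exactly 1. The one-sided 0.05 figures of 34% and 92% overstate the risk under the planned reporting, where they become 23% and 85%. The SCRI is the secondary design, so this bears on how its ratio is interpreted and leaves the primary cohort comparison untouched.

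**What to change.** 1. In Section 9.1.2, limit the statement on other vaccination to vaccines given on days other than the ABRYSVO date.
2. In Sections 9.2.3 and 9.7.2.3, add an SCRI in recipients with no other vaccine on day 0. Report it beside the all-recipient and co-administered SCRI, with interval counts, and name it as the estimate that same-day vaccines cannot confound.
3. Define that stratum on day 0 only. Requiring no other vaccine through day 10 would condition on behaviour after the index date. A person with an early event may put off a later vaccine and be kept, while a person vaccinated on day 5 with an event on day 9 would be dropped. That can remove control-interval events selectively and inflate the ratio.
4. In Section 9.9, list same-day co-administration as a limitation of the SCRI. Note that contrasting the ABRYSVO-alone and co-administered ratios compares different people.

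The cost is a few sentences and one stratified rerun on data the study already holds. The ABRYSVO-alone stratum will have fewer events and a wider CI. At c = 50%, about twice as many recipients are needed overall to keep the Table 3 precision in that stratum.

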9.1.3. Medical Records Review

Cases of atrial fibrillation among individuals vaccinated with ABRYSVO will be validated/adjudicated (see Section 9.7.2.4 Case Validation/Adjudication via Medical Records Review for further details). VA analysts will produce a line listing of cases for medical records data abstraction. The listing will contain an identifier and other relevant information

that is sufficient to identify the correct EHR for each patient (detailed in Section 9.6.1 "Case Report Forms (CRF)"). The listing will also include sex, date of birth, date of vaccination with ABRYSVO, date of atrial fibrillation diagnosis, age at diagnosis of atrial fibrillation, days lapsed since vaccination, and co-administered vaccines.

9.2. Setting

The study population will consist of individuals aged 18 years and older within the VHA system from 31 May 2023 to 31 May 2026.

9.2.1. Inclusion Criteria

Three cohorts will be defined for the main analyses.

- A. A cohort of individuals who received ABRYSVO will form the ABRYSVO cohort and must have:
 - A record for at least one dose of ABRYSVO in the study period from 31 May 2023 (or earliest date of vaccine availability for the indicated population) to 31 May 2026; the date of ABRYSVO vaccination will define the index date for this cohort
 - o No record of an RSV vaccine from a manufacturer other than Pfizer
- B. A cohort of individuals who did not receive ABRYSVO but received another vaccine will form the contemporary vaccinated control cohort and must have:
 - A record for another vaccine (eg, influenza vaccine, COVID-19 vaccine, and other pre-specified vaccines such as shingles, hepatitis B listed in Section 9.3.3) within 30 days of a corresponding ABRYSVO vaccinee's vaccination date; the control's index date will be the date of the control's non-RSV vaccine
 - No record for any RSV vaccine on the index date or in the baseline period (ie, 2 years prior to the index date)
 - Individuals in the vaccinated control cohort who go on to receive an RSV vaccine following their index date will be censored at the time of RSV vaccination. If the RSV vaccine is ABRYSVO, these individuals will contribute to the ABRYSVO cohort starting from the date of ABRYSVO receipt.
- C. A cohort of individuals who did not receive ABRYSVO or another vaccine on the index date but had at least one vaccination record in the year prior to the index date will form the contemporary unvaccinated control cohort and must have:
 - No record for any RSV vaccine on or within 30 days of the index date or in the baseline period (ie, 2 years prior to the index date)

- No record for any other vaccine (eg, those listed in Section 9.3.3) on or within 30 days of the index date
 - This cohort will be assigned an index date matched to a corresponding ABRYSVO vaccinee's vaccination date. If the vaccination is associated with a healthcare encounter (ie, inpatient [IP] or outpatient [OP] visit), the unvaccinated control will be required to have a healthcare encounter within 30 days of the assigned index date, and the date of the healthcare encounter will be set as the index date for the unvaccinated control.
 - Individuals in the unvaccinated control cohort who go on to receive an RSV vaccine following their index date will be censored at the time of RSV vaccination. If the RSV vaccine is ABRYSVO, these individuals will contribute to the ABRYSVO cohort starting from the date of ABRYSVO receipt.
- o Regular use of preventive medical care, defined as at least one vaccination record between 365 to 31 days prior to the index date.

In addition, individuals in all cohorts must meet the following inclusion criteria to be eligible for the study:

- At least 2 years of continuous enrollment in (ie, no disenrollment from) VHA benefits (ie, the baseline period) prior to the index date
- Complete follow-up (ie, no disenrollment from VHA benefits, death, or receipt of RSV vaccination [for controls who may later receive any RSV vaccine only]) during the risk interval and confirmatory diagnosis window (eg, 34 days of complete follow-up for 0-3 days primary risk interval plus 30-day confirmatory diagnosis window; or 32 days or 61 days for secondary analysis with 0-1 days and 0-30 days risk intervals plus 30-day confirmatory diagnosis window, respectively).

Based on age on the index date, eligible individuals will be further classified into the following two age groups with the following additional inclusion criteria:

- 18-59 years old age group
 - o 18-59 years of age on the index date
 - o For individuals in cohorts B and C, a record for specific conditions that increase the risk for severe RSV as defined by the CDC during the baseline period, identified as those with chronic cardiovascular disease, chronic lung or respiratory disease, end-stage renal disease or dependence on hemodialysis or other renal replacement therapy, diabetes mellitus with complications, neurologic or neuromuscular conditions causing impaired airway clearance or respiratory muscle weakness, chronic liver disease, chronic hematologic

conditions, severe obesity, moderate or severe immune compromise, residence in a nursing home, or other chronic medical conditions or risk factors that a health care provider determines would increase the risk for severe disease due to viral respiratory infection (eg, frailty); list of conditions may be updated to align with the most current CDC definition at the time of data analysis¹⁹

- Moderate and severe immunocompromising conditions will include solid tumor and hematologic malignancies, receipt of solid-organ transplant or an islet transplant, receipt of chimeric antigen receptor (CAR) T-cell therapy or hematopoietic cell transplant (HCT) (within 2 years of transplantation), moderate or severe primary immunodeficiency, and human immunodeficiency virus [HIV] infection)¹⁹
- 60 years and older age group
 - o At least 60 years of age on the index date

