 - 2) Secondary analysis individuals who were not vaccinated with any vaccine on the index date but had at least one vaccination record in the year prior to the index date (ie, contemporaneous unvaccinated control cohort)
- An self-controlled risk interval (SCRI) design, which will serve as the secondary study design, will be used to compare the incidence of atrial fibrillation and supraventricular arrhythmia during the post-vaccination risk window (eg, 0-3 days following vaccination) to the post-vaccination control window (eg, 4-10 days following vaccination) among ABRYSVO vaccinated individuals.
- Medical records review will be conducted as a separate component to validate/adjudicate cases of atrial fibrillation among ABRYSVO vaccinated individuals within the VHA system.

Population: The study population will consist of individuals with a record of at least one dose of ABRYSVO who are at least 18 years of age on the date of vaccination (ie, index date). Individuals who receive an RSV vaccine from a manufacturer other than Pfizer will be excluded from the study. Contemporary vaccinated controls will be included if they have no record of RSV vaccine and have a record for another vaccine (eg, influenza vaccine, COVID-19 vaccine, and other pre-specified vaccines such as shingles, hepatitis B) within 30 days of a corresponding ABRYSVO vaccinee's vaccination date; the control's index date will be the date of the control's non-RSV vaccine and they will be required to be at least 18 years of age on the index date. Contemporary unvaccinated controls will be included if they have no

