As a secondary analysis, individuals who received ABRYSVO will be compared to individuals not receiving any vaccinations at that point in time but had at least one vaccination record in the year prior to the index date (ie, contemporary unvaccinated controls). The unvaccinated controls will be assigned an index date matched to a corresponding ABRYSVO vaccinee's vaccination date; these individuals can later receive ABRYSVO and enter the vaccination group if all eligibility criteria are met. To address possible selection bias due to health seeking behaviors, the unvaccinated controls will be randomly selected from a population of patients who have regular use of preventive medical care within the VHA system, defined as at least one vaccination record in the year prior to the index date. The index date for the contemporary unvaccinated controls will be selected based on the observed index dates in the vaccinated cohort. If ABRYSVO vaccination is associated with a regular healthcare encounter, the contemporary unvaccinated control will be required to have an encounter within 30 days of the assigned index date, and the date of encounter will be set as the index date to ensure comparability of covariate measurement.

In the primary analysis, the ABRYSVO vaccinated, contemporary vaccinated control, and contemporary unvaccinated control cohorts will be followed for up to 34 days post-index (ie, 0-3 day risk interval plus 30-day diagnosis confirmation window) to assess and confirm the occurrence of atrial fibrillation and supraventricular arrhythmia. In secondary analyses, the cohorts will be followed up to 32 days post-index (ie, 0-1 day risk interval plus 30-day diagnosis confirmation window) and up to 61 days post-index (ie, 0-30 day risk interval plus 30-day diagnosis confirmation window). Individuals will be censored upon the earliest occurrence of disenrollment, death, date of RSV vaccination (for controls who later receive any RSV vaccine only), or end of the risk window. The date of the first atrial fibrillation (or supraventricular arrythmia) case will be considered date of onset.

[figure not shown]

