To reduce possible outcome misclassification, confirmatory diagnosis of atrial fibrillation and supraventricular arrhythmia will be required within 30 days of the initial diagnosis. In PFIZER CONFIDENTIAL

addition, chart review adjudication will be used to ensure a high PPV for identifying atrial fibrillation. If the PPV is not considered high enough, the algorithm used to identify incident atrial fibrillation using codified data may be updated in subsequent analyses.

The study population has been kept as broad as possible in order to capture safety events that occur among all individuals vaccinated with ABRYSVO. However, individuals who ever had a record of RSV vaccine from a different manufacturer are excluded to ensure that safety signals are not attributable to different RSV vaccines. Thus, the study results are not generalizable to patients who received RSV vaccines from different manufacturers.

The VHA CDW provides a range of benefits, including its comprehensive structure, large number of variables, and electronic accessibility. The VHA CDW also includes EHR data that include structured fields and open fields (such as physician notes, which will be used for case validation, as needed). Importantly, the VHA CDW retains electronic immunization records that include manufacturer name and lot numbers, facilitating the identification of brand-specific vaccines, such as ABRYSVO. Moreover, the VHA CDW data are updated on a daily basis.

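### The exclusion of ABRYSVO recipients for another manufacturer's RSV vaccine has no date anchor, so cohort membership depends on vaccinations given long after the outcome window

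*Protocol*

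**What the plan says.** Section 9.2.1 sets one criterion for the ABRYSVO cohort (cohort A) on other brands: "No record of an RSV vaccine from a manufacturer other than Pfizer". It gives no window. Section 9.9 restates the rule as "individuals who ever had a record of RSV vaccine from a different manufacturer are excluded", so that a signal cannot be attributed to a different RSV vaccine. The Abstract (Population) says "Individuals who receive an RSV vaccine from a manufacturer other than Pfizer will be excluded from the study".

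Controls have dated rules. Vaccinated controls (cohort B) need "No record for any RSV vaccine on the index date or in the baseline period", the baseline being the two years before index. Unvaccinated controls (cohort C) have the same look-back plus 30 days around the index date. Later receipt by controls leads to censoring: cohort B members who receive an RSV vaccine "following their index date will be censored at the time of RSV vaccination", and cohort C has the same provision. Section 9.1.1 lists among its censoring events "date of RSV vaccination (for controls who later receive any RSV vaccine only".

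Section 9.2.1 also requires complete follow-up in all cohorts over the risk interval and confirmation window (34 days in the primary analysis). Its RSV-vaccination condition applies to controls alone, and the Abstract repeats this. Yet the Abstract also says "Contemporary vaccinated controls will be included if they have no record of RSV vaccine", without a window.

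**The concern.** Eligibility for a cohort should be settled by what is known at index, or at the latest by the end of required follow-up. Here an ABRYSVO recipient can pass every criterion, complete the 34 days with or without atrial fibrillation, and then be deleted because of a vaccine chosen much later. If new atrial fibrillation changes the chance of that later vaccination, cases and non-cases are deleted at different rates and the observed incidence shifts. Illness or death could lower the chance; a new cardiovascular diagnosis could raise it, since chronic cardiovascular disease is among the listed conditions for severe RSV.

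The stated purpose does not need this. A vaccine given after the risk interval cannot cause an event inside it.

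At stake are the ABRYSVO incidence rate, which is the primary objective, and the hazard ratio against controls, who are not subject to the same deletion. Section 9.5 plans analyses at two time points, so a vaccination counted in the interim report can also disappear from the final one.

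**Working it through.** **1. The rules side by side, for receipt of another manufacturer's RSV vaccine (primary analysis).**

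| Timing of receipt | Cohort A | Cohorts B and C |
|---|---|---|
| On index, or in the 2 years before | Excluded | Excluded |
| After index, to day 33 | Excluded | Excluded by the complete follow-up criterion; censored by the cohort text and section 9.1.1 |
| After day 33 | Excluded, no end date | Retained in full |

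For cohort C the 30-day bar around index also excludes within the middle row. The last row is the asymmetry at issue. No passage limits the rule for cohort A, because the follow-up condition and the censoring event on RSV vaccination are both confined to controls.

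**2. How far ahead the rule can look.** Take an index date of 31 May 2023, the first day of the study period (section 9.2.1). The risk interval ends on day 3 and required follow-up on day 33 (34 days counting day 0).

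- To the end of the study period, 31 May 2026: 1,096 days from index. That is 1,096 - 3 = 1,093 days after the risk interval and 1,096 - 33 = 1,063 days after required follow-up.
- To the planned data cut, 30 November 2027 (section 6): 1,644 days from index. That is 1,641 and 1,611 days.

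With the rule tied to required follow-up, the longest look-ahead would be day 33 (day 31 or day 60 in the secondary analyses).

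**3. Size.** The protocol states no figure to reproduce. Let q be the share of ABRYSVO recipients later given another brand, and r that probability in atrial fibrillation cases relative to non-cases. Cases are rare: 33.9 per 1,000 person-years over 4 days is 0.0339 × 4 / 365.25 = 0.00037. Person-time is therefore reduced by almost exactly 1 - q and cases by 1 - rq:

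factor on the ABRYSVO rate = (1 - rq) / (1 - q)

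Both q and r are assumptions.

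| q | r = 0.5 | r = 1.5 |
|---|---|---|
| 0.5% | 0.9975 / 0.995 = 1.0025 | 0.9925 / 0.995 = 0.9975 |
| 5% | 0.975 / 0.95 = 1.026 | 0.925 / 0.95 = 0.974 |

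In the extreme where everyone removed is event-free (r = 0), the factor is 1 / 0.995 = 1.005 to 1 / 0.95 = 1.053. The hazard ratio moves by about the same factor, as far as the weighted covariates do not explain the difference in later uptake.

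**4. Lost numbers.** To keep 37,444 vaccinees (section 9.5.1, age 60 and over, 2-fold increase, 4:1), 37,444 / 0.995 = 37,633 to 37,444 / 0.95 = 39,415 would be needed.

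**The case against.** The strongest reply is that this is a wording matter of little consequence. The cohort A line binds ABRYSVO recipients only, and different cohorts may have different rules. Few people may ever receive a second RSV vaccine of another brand, since section 7 describes a single dose. The study highlights 1.5-fold and 2-fold increases, against which a few per cent is minor. All of this stands as regards size. It does not supply the missing date or justify conditioning on the future.

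Four stronger readings are tempting and are not supported:

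- *The cohort A exclusion contradicts the censoring of controls.* It does not; it is an asymmetry between cohorts.
- *Controls are also deleted for any later receipt, with a larger effect on the hazard ratio.* The exclusion sentence in the Abstract directly follows the definition of the ABRYSVO population, and the one in section 9.9 follows a sentence about ABRYSVO vaccinees. The Abstract itself provides for controls who later receive an RSV vaccine. For later receipt by controls, section 9.2.1 is clear.
- *The self-controlled analysis is biased.* Everyone in it is a case. Bias would need later other-brand uptake to differ between cases on days 0-3 and cases on days 4-10, and nothing shows that. Losing cases costs precision.
- *The look-ahead certainly runs to 30 November 2027.* That is an inference. No passage says that vaccine records after 31 May 2026 decide eligibility.

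**Conclusion.** The point holds for cohort A. The exclusion is undated, section 9.9 makes it open-ended, and ABRYSVO recipients with valid, completed follow-up are removed for later behaviour that cannot bear on their outcome. Controls are not treated in this way. The effect on the primary incidence rate and the hazard ratio is probably small, a factor of about 0.97 to 1.03. That rests on an assumed later uptake of up to 5% and an assumed relative probability of 0.5 to 1.5; the documents give neither, and the direction is unknown. The reason to act is that the dependence is avoidable and lets cohort membership change between reports.

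Two wording faults go with it. The Abstract's requirement of no RSV record for vaccinated controls does not fit its own provision for later receipt, nor section 9.2.1. Separately, RSV vaccination of a control during the follow-up window leads to exclusion under the complete follow-up criterion (9.2.1 and Abstract) but to censoring under the cohort text and section 9.1.1.

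**What to change.** 1. In section 9.2.1, cohort A: require no RSV vaccine from another manufacturer on or before the index date.
2. For receipt after index but within the risk interval and confirmation window, apply the same rule to cohort A as to controls. Extend the controls-only clause in the Abstract, section 9.1.1 and the complete follow-up criterion of 9.2.1 to other-manufacturer receipt in cohort A.
3. Decide whether that common rule is exclusion or censoring, and reconcile the complete follow-up criterion (9.2.1, Abstract) with the censoring text (9.1.1, cohorts B and C). Adding a censoring rule for cohort A alone would leave this conflict in place.
4. Ignore receipt after the window in every cohort.
5. Align the exclusion sentences in the Abstract and section 9.9, and date the Abstract's no-RSV-record condition for vaccinated controls as in 9.2.1.

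The cost is wording in the Abstract and sections 9.1.1, 9.2.1 and 9.9, and a changed date condition in the cohort program. No new data are needed, and vaccinees who would otherwise be lost are kept.
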